**Table 2-5 Nerve Conduction Safety Parameters**

Maximum of 3 measures performed per nerve
1a Sural SNAP Measurement #1 #2 #3
1b Sural Sensory NCV measurement #1 #2 #3
2a Tibial CMAP measurement #1 #2 #3
3b Tibial Motor NCV measurement #1 #2 #3

Numbers with a/b refer to the fact that these measurements are yielded from one and the same stimulation.

There are four parameters included in NCS indicated in [Table 2-5](#), each will be measured three times on either laterality or both. For each parameter, per visit, the max value will be derived to calculate change from baseline:

Change = max (post-BL measurement #1, #2, #3) - max (BL measurement #1, #2, #3)

Note that, if a measurement is not repeated three times, max will be derived using available measurements (maybe less than three times).

The following flags and analyses will be created to capture worsening and recovery for each parameter by laterality: SNAP, sural NVC, tibial NCV and CMAP:

Flags by visit level:

- By visit flag 1:  $\geq 50\%$  reduction
- By visit flag 2 (recovery): For participants who met the criterion flag1 reduction  $\geq 50\%$ : Flag the visits after last visit with reduction  $\geq 50\%$  that the criteria (reduction  $\geq 50\%$ ) is no longer met

Flags by participant level for each parameter SNAP, sural NVC, tibial NCV and CMAP based on the above visit-based:

- Participant level flag 1: participants without any reduction  $\geq 50\%$  at any visit on any side
- Participant level flag 2: participants with a reduction of  $\geq 50\%$  at any visit on any side
- Participant level flag 3: participants with reduction of  $\geq 50\%$  at any visit and followed by recovery for all the side(s) that had worsening

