#### **2.7.4.4 Neurological Exam**

Neurological examinations are conducted at each visit to monitor for any clinically significant abnormalities. The exam has three subcategories: Motor function, Deep tendon reflexes and Sensory system. Each subcategory includes multiple exams on various body locations. AE and SAE will be reported respectively in case of clinically significant findings.

A worsening at post BL is defined as: a decrease from baseline and the score is **NOT** normal. In order to systematically summarize the worsening from baseline, the following flags will be created to capture different degrees of worsening and recovery:

Flags by visit and by parameter level:

- By visit flag 1 (worsening): reduced grade (decrease) in at least 2 consecutive visits post BL (same worsening at the same parameter/location/laterality). Flag the last visits with worsening.
- By visit flag 2 (recovery): For participants who met the criterion for 2 consecutive visits, flag visits after **last** visit with worsening (this worsening stands for any worsening and don't have to be consecutive) that the grade is back to baseline

Flags by participant level and by three **subcategories** based on the above visit-based:

- participant level flag 1: Participant without any worsening at 2 consecutive visits by Motor function, DTR, and Sensory
- participant level flag 1.5: Participant without any worsening at 2 consecutive visits in any subcategory
- participant level flag 2 (worsening): Participant with any worsening at 2 consecutive visits by Motor function, DTR and Sensory
- participant level flag 3 (recovery): Participant with any worsening at 2 consecutive visits followed by recovery (worsening no longer present in all parameters within the category) by Motor function, DTR and Sensory
- participant level flag 4 (partial recovery): Participant with any worsening at 2 consecutive visits followed by partial recovery (worsening no longer present in at least one of the parameters within the category) by Motor function, DTR and Sensory
- participant level flag 5 (overall worsening): Participant with worsening at 2 consecutive visits in any subcategory
- participant level flag 6 (overall recovery): Participant with worsening at 2 consecutive visits in any subcategory followed by recovery (recovered in all parameters)

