#### 2.7.4.5 Neuropathy questionnaire

For neuropathy symptoms: worsening is defined for participants with a change in answer from “No” at baseline to “Yes” at post BL.

Flags by visit and by parameter level:

- By visit flag 1: adverse change indicated by a “YES” response to the same question in the questionnaire in at least 2 consecutive visits. flag the last visit with finding
- By visit flag 2: adverse change indicated by a “YES” response to a question in the questionnaire at any post baseline visit
- By visit flag 3 (recovery): Flag visits after **last** visit with finding (this finding stands for any worsening and don’t have to be consecutive) that the answer is back to baseline

Flags by participant level based on the above visit-based:

- Participant level flag 1: Participant without any finding at 2 consecutive visits
- Participant level flag 2: participants with any finding at 2 consecutive visits

- Participant level flag 3 (recovery): participants with any finding at 2 consecutive visits and followed by recovery (finding no longer present in all worsened questionnaire)
- Participant level flag 4 (partial recovery): participants with any finding at 2 consecutive visits and followed by partial recovery (finding no longer present in at least one of the worsened questionnaire)
- Participant level flag 4: Participant without any finding at any visit
- Participant level flag 5: participants with any finding at any visit
- Participant level flag 6 (recovery): participants with any finding and followed by recovery (finding no longer present in all worsened questionnaire)

Participant level flag 6.5 (partial recovery): participants with any finding and followed by partial recovery (finding no longer present in at least one of the worsened questionnaire) Note that, flags will be created based on weekly basis window instead of protocol scheduled visit window.

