### 2.7.4.6 Nerve conduction study (NCS)

NCS are conducted at baseline and repeated in every patient as per USM.

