#### 2.7.4.7 Overall safety findings and recovery

Results from Neuro findings including: NCS, neuro exam, symptoms (AEs and neuro questionnaire) will be summarized in one table for participants on active to show number (%) of participants with finding together with the information about recovery (yes/no) at the end of observation.

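### NCS recovery in the SAP means only that a loss of 50% or more is no longer present, yet it shares a yes/no recovery table with measures that must return to baseline or normal

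*SAP*

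**What the plan says.** **NCS (SAP 2.7.4.6).** At each visit the largest of up to three readings is compared with the largest baseline reading, for sural SNAP, sural NCV, tibial CMAP and tibial NCV, by side. A finding is a reduction of at least 50%. For participants with a finding, the visit-level recovery instruction is "Flag the visits after last visit with reduction" of at least 50%, where that criterion is no longer satisfied. At participant level the finding must be "followed by recovery for all the side(s) that had worsening". No minimum improvement, return to baseline, normal limit or confirming visit is required. The tables in this section are counts and frequencies only.

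**Neurological exam (SAP 2.7.4.4).** A participant enters with the same worsening, at the same parameter, location and side, at two or more consecutive visits. Visit-level recovery requires "that the grade is back to baseline". The participant-level wording is "worsening no longer present in all parameters within the category". The definition of worsening runs "A worsening at post BL is defined as: a decrease from baseline and the score is" not normal.

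**Questionnaire (SAP 2.7.4.5).** Worsening is a change from No to Yes. Recovery requires "that the answer is back to baseline".

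**Combined table (SAP 2.7.4.7).** NCS, exam, adverse events and questionnaire appear in one table for participants on active drug, giving the number with a finding "together with the information about recovery (yes/no) at the end of observation". No common definition of recovery and no caveat is given.

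**The concern.** One word carries two meanings in one table. On the exam and questionnaire rows, recovered means that the participant is back at the starting grade or answer, or for the exam no longer worse than baseline in a way that is abnormal. On the NCS row it can mean that almost half of the baseline value is still missing. Protocol 8.4.4 says that screening NCS results should be normal, so that residual loss is measured against a baseline meant to be healthy.

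The Amendment 02 rationale says that participants on branaplam were asked to stay for about a year after stopping treatment, specifically to follow signs and symptoms of peripheral neuropathy and to collect further MRI data. The 2.7.4.7 table draws the neuropathy part of that follow-up together. If its NCS row is read like the rows beside it, nerve damage will look more reversible than the data show.

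**Working it through.** The SAP states no figure to reproduce. The check applies its definition directly.

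**Inputs.** The finding threshold and recovery rule are from SAP 2.7.4.6. Percent change is (post-baseline − baseline)/baseline × 100%, from SAP 2.1.1. No assumption about measurement variability is used.

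**Step 1: what the rule requires.** A worst loss of L% (L ≥ 50) leaves (100 − L)% of baseline. The criterion stops being met just above 50% of baseline. The minimum regain is therefore just over L − 50 points of baseline, which is (L − 50)/L of what was lost. The rise relative to the worst value is 50/(100 − L) − 1 to lose the flag, and 100/(100 − L) − 1 to reach baseline.

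| Worst loss L | Share of loss to regain, (L − 50)/L | Rise to lose the flag | Rise to reach baseline |
|---|---|---|---|
| 51% | 1/51 = 2.0% | 2% | 104% |
| 55% | 5/55 = 9.1% | 11% | 122% |
| 60% | 10/60 = 16.7% | 25% | 150% |
| 70% | 20/70 = 28.6% | 67% | 233% |
| 80% | 30/80 = 37.5% | 150% | 400% |
| 100% | 50/100 = 50.0% | not defined | not defined |

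L cannot exceed 100, so the required share never exceeds about half.

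**Step 2: the rule on example values** (baseline 10.0, chosen for illustration):

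- 4.9 then 5.1 (51% then 49% loss): recovered.
- 3.0 then 5.1 (70% then 49% loss): recovered.
- 4.9 then 10.0 (51% then 0% loss): recovered.
- 4.9 then 4.9 (51% throughout): not recovered.

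The first three participants are indistinguishable in a yes/no table.

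**Step 3: the other rows.** The questionnaire is binary, so leaving the finding state is the same as returning to baseline. For the exam, losing the finding means a grade at or above baseline, or a normal one. Only on the NCS row does losing the finding leave room for a large residual deficit.

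**Step 4: leverage of one participant.** The Amendment 02 rationale reports 7 active participants with a 50% decrease in sural SNAP. On that count, each participant placed in or out of the recovered group moves the SNAP recovery rate by 1/7 = 14.3 percentage points. This is a December 2022 figure, and the final denominator may differ.

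**The case against.** The strongest reply is that the rule is stated openly and follows a consistent convention: recovery is the absence of the entry criterion. Serum NfL in SAP 2.11.1 works the same way, so a value at 1.9 times baseline and not above 100 pg/mL counts as recovered. The exam and questionnaire return to baseline because they are graded or binary, not because NCS was given a deliberately softer rule. That is correct, and a reader should not infer an intent to flatter the NCS result. But serum NfL is not among the measures named for the combined table, and raw values, changes and individual plots are planned for it. For NCS only counts and a listing are planned.

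The second reply is that the listings already carry the information. SAP 5.4 says that listings include all assessments, and 2.7.4.6 lists participants and parameters with findings, so residual loss should be visible person by person. This stands, and it lowers the stakes. It does not alter the count in the summary table.

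Third, the comparison has limits. The exam requires two consecutive worsened visits to enter, so its entry rule is not simply any decrease. The exam and questionnaire also have partial-recovery flags, and 2.7.4.7 does not say how those map to yes/no. Nor does 2.7.4.7 name the NCS flag that it uses; participant-level flag 3 is the likely source, but that is an inference.

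Fourth, nothing is tested. All analyses are descriptive, and development in Huntington's disease has already stopped. This stands too: no inference or dosing decision turns on the flag.

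**Conclusion.** The point holds as a fault in how a summary measure is defined and labelled, and it should be corrected. By definition alone, NCS recovery allows a residual loss of just under 50% and never requires more than about half of the loss to be regained. Recovered is therefore materially weaker on the NCS row than on the exam and questionnaire rows. The conclusion assumes that percent reduction follows the general formula in SAP 2.1.1, and that 2.7.4.7 uses the only NCS recovery definition the SAP gives.

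Three stronger readings are not supported:

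- *That participants will in fact be misdescribed, or that measurement noise alone will produce recoveries.* The documents give no individual NCS values and no variability, so the number affected is unknown.
- *That a brief dip below the threshold is enough, or that missing NCS follow-up drives the result.* Recovery must come after the last visit with a reduction of at least 50%, on every worsened side. The SAP also says "NCS are conducted at baseline and repeated in every patient as per USM", and Protocol Table 8-5 schedules NCS at Weeks 33, 53 and 69.
- *That CSF NfL has a matching fault, with participants who have no later sample falling to no.* SAP 2.11.1 states no such default. The missing-data text in SAP 2.5.4 belongs to the primary endpoint. At most the handling is unspecified, and that is a different problem from this one.

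**What to change.** 1. In the tables of SAP 2.7.4.6 and 2.7.4.7, label the NCS flag *≥50% reduction no longer met* in place of recovery.
2. For each participant with an NCS finding, show the residual percentage of baseline at the last assessment, by parameter and side, with weeks since last dose.

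Any numerical cut for full NCS recovery is for the sponsor to set; none is proposed here.

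The cost is SAP text, table labels and one extra column. No new data are needed. The one downside for the sponsor is that the NCS row may look less favourable once residual loss is shown.

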#### Tables

- For each parameter, summary tables showing number and frequencies of participants with reduction of  $\geq 50\%$  at any visit, and followed by recovery and partial recovery

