The **USM Follow-up IN (06-Dec-2022)** was issued by Novartis to inform investigators that Novartis has decided to discontinue development of branaplam as a potential treatment for people with Huntington's disease. The decision followed a review of unblinded data from VIBRANT-HD indicating that the benefit:risk of branaplam in Huntington's disease is not positive. This decision was endorsed by the independent Data Monitoring Committee (DMC) as well as the VIBRANT-HD SC.

Key findings from this review included:

- Increased NfL levels in serum and/or cerebrospinal fluid (CSF) observed in the majority of the participants in active arm.
- Changes in the neurological exam on two consecutive visits, predominantly new hypoactive and/or absent DTRs, observed in more than half of participants in the active arm and the majority of participants with 12 weeks or more of treatment.
- Almost half of the participants in the active arm reported symptoms of peripheral neuropathy, either through the neuropathy questionnaire or as an adverse event report.
- Decreased amplitude (50%) in the sural nerve (SNAP) compared to baseline was observed in 7 participants in active arm.
- Preliminary magnetic resonance imaging (MRI) findings suggestive of an increased volume of the lateral ventricles were seen in majority of patients in active arm.
- Steady state mutant HTT lowering in CSF estimated to be approximately 30% with weekly doses of 56 mg branaplam.

Given the high incidence of signs/symptoms of neurotoxicity at the current dose of branaplam, it is considered highly unlikely that lower doses or different dose regimens can be identified that would be safe and provide clinically meaningful benefit.

With the **USM (06-Dec-2022)** letter, study drug is now permanently discontinued in the VIBRANT-HD study and no further cohorts will be initiated. Both the DMC and the SC recommended that all participants who received active treatment (branaplam) remain in the study for follow-up for approximately one year following initial treatment discontinuation, specifically to continue to assess signs and symptoms of peripheral neuropathy as well as to collect additional MRI data.

Additionally, the allocation to treatment (branaplam or placebo) for each of the participants at the sites was provided to investigators in separate communications.

The following actions were to be taken by sites as part of the update to the USM in the VIBRANT-HD study:

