#### 2.1.1 General definitions

##### Treatment groups

Due to USM, only Cohort 1 was initiated. All analysis will be performed by treatment group within cohort 1:

- Cohort 1: LMI070 56 mg and Placebo

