#### Listings

Listing will be provided for participants and parameters with findings.

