**Note that NFL (both serum and CSF) will be considered as safety parameters (the higher the worse).**

For tables displaying the worst-case scenario for safety assessment, all assessments within a visit window will be used to identify the worst.

Listings will include all assessments, sorted by date of assessment, flagging unscheduled visits. The listings will flag to indicate the assessment's inclusion in the analysis.

In the below tables, the end of Core period is defined as the day of last assessment for Core period and the end of OLE is defined as the day of last assessment for OLE.

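### Nerve conduction results are tabulated only as reductions of 50% or more, so smaller losses and partial return towards baseline are not shown, although change from baseline is already derived

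*SAP*

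**What the plan says.** SAP 2.7.4.6 covers sural SNAP, sural NCV, tibial CMAP and tibial NCV. It takes the largest of up to three readings: "For each parameter, per visit, the max value will be derived to calculate change from baseline". The visit flags then mark a reduction of 50% or more, and recovery as any visit after the last such reduction at which the criterion is no longer met. The same cut serves amplitudes and velocities: "Flags by participant level for each parameter SNAP, sural NVC, tibial NCV and CMAP based on the above visit-based".

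The planned outputs are one table, "For each parameter, summary tables showing number and frequencies of participants with reduction of" at least 50% at any visit with recovery and partial recovery, and one listing: "Listing will be provided for participants and parameters with findings". The table promises partial recovery, but the section defines no flag for it. SAP 2.7.4.7 carries NCS findings and recovery into a combined neurological table for active participants only.

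The Protocol (Amendment 02 rationale) reports from the unblinded review: "Decreased amplitude (50%) in the sural nerve (SNAP) compared to baseline was observed in 7 participants in active arm".

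**The concern.** After treatment was stopped, participants on branaplam were asked to stay about a year, specifically to assess signs and symptoms of peripheral neuropathy and to collect more MRI data (Protocol, Amendment 02 rationale). NCS is scheduled at Weeks 33, 53 and 69 (Protocol Table 8-5). Two questions follow: how much nerve function was lost, and how much came back. A count at a 50% cut answers neither. It does not show the size of losses short of 50%, and it cannot grade recovery.

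The SAP treats its other continuous data differently. Laboratory tests, ECG, vital signs and NfL get values and change from baseline by visit. MRI volumes and CSF mHTT also get % change. NCS already has visit windows (SAP Table 5-2) and an on/off-treatment flag (SAP 2.1.1). The SAP gives no reason for leaving it out.

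**Working it through.** **Step 1. What each output would show.** The documents give no power or precision figure for NCS, so there is none to reproduce. Take one amplitude with a hypothetical baseline of 100 units:

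| Post-baseline course | Table | Listing |
|---|---|---|
| 51 throughout (49% loss) | no reduction of 50% or more | not listed |
| 50, then 51 | reduction, then recovery | listed |
| 50, then 100 | reduction, then recovery | listed |

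The first course is tabulated like no loss at all. The second and third fall in the same table row, although one has barely changed and the other is back at baseline.

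**Step 2. Amplitude losses below the cut (illustration).** The documents give no SD, so these are assumed. With % loss normal, mean m and SD s, P(loss ≥50%) at one visit = 1 − Φ((50 − m)/s). About 20 active participants follow from about 25 per arm at 4:1 (Protocol 3 and 6.3.2).
- m = 25, s = 10: P = 0.006, so 0.1 of 20 expected to be flagged.
- m = 30, s = 15: P = 0.091, so 1.8 of 20.
- m = 40, s = 15: P = 0.252, so 5.0 of 20.

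Counting any visit and either side would raise these counts. It would still not show the size of the losses.

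**Step 3. Velocity.** With a true mean slowing of 20% and log-SD d, P(loss ≥50%) = Φ((ln 0.5 − ln 0.8)/d) = Φ(−0.470/d).
- d = 0.05 or 0.10: at most 0.0001% per participant.
- d = 0.15: Φ(−3.13) = 0.086% per participant; for any of 20, 1 − (1 − 0.00086)^20 = 1.7%.

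On an additive scale with the same mean, the chance that any of 20 is flagged is 2.7% at an SD of 10 points and 37% at 15 points. The result therefore depends on velocity varying modestly, which the documents neither state nor contradict.

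**Step 4. Between-arm contrast, illustrative only.** Inputs are 7 active participants with SNAP loss (Protocol), 20 and 5 participants (planned, assumed to be the denominators) and 0 on placebo (assumed; no placebo count is given). Fisher's exact test of 7/20 against 0/5 gives p = 0.27; 11/20 against 0/5 would be needed for p < 0.05 (p = 0.046).
- If 35% is taken as a single-visit rate, with assumed active log-SD 0.3 to 0.7 and placebo log-SD 0.2 to 0.3, power at two-sided 5% is about 5% for the flag and 48% to 99% for a Welch test on the log ratio.
- The planned flag is any visit, any side. If 35% is instead the rate over any of three tests (assumed correlation 0.5), the single-visit Welch power falls to about 5% to 90%.
- If only 12 active participants had been tested, 7/12 against 0/5 gives p = 0.044.
- At 20 against 5 with 0% on placebo, flag power is 41%, 76% and 95% at true active rates of 50%, 60% and 70%.

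The comparison moves too far with the assumptions to give a firm size for the loss.

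**The case against.** **No between-arm test is planned.** The SAP is descriptive and serves an abbreviated report written after development stopped. This stands. A reader might infer that nearly all ability to separate branaplam from placebo is lost; the documents do not support that. Step 4 shows the answer turning on SDs, denominators and a placebo count that are not given.

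**The placebo contrast is weak anyway.** There are about five placebo participants, NCS before the safety measure was repeated only on findings or investigator judgement (Protocol Table 8-2), and placebo participants leave by Week 33. This stands, and tabulating change would not cure it. It does not touch the value of describing the active arm over time.

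**Smaller losses are not invisible.** Site specialists interpret the tests, clinically significant results become adverse events, and SAP Table 2-3 already holds an axonal nerve conduction change reported this way. Serum NfL is also summarised by visit. This stands in part: such events reach tables and listings without the 50% cut, but only when judged clinically significant, and without the measured values.

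**The cut matches the unblinded review.** It does match that review's SNAP finding, which is a good reason to keep the count. It is not a reason to report nothing else, and the finding concerned SNAP, not velocity.

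**The listing may be complete.** SAP 5.4 says "Listings will include all assessments, sorted by date of assessment, flagging unscheduled visits". That general rule does not clearly override the specific limit in 2.7.4.6, where findings are not further defined. At most it leaves the listing ambiguous.

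**Conclusion.** The point holds as a gap in reporting. Change from baseline is derived for four NCS parameters and no planned output shows it. Losses below 50% appear in no NCS output unless reported as adverse events, and recovery cannot be told from a small shift across the cut. Both follow from the text and need no assumption.

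The velocity rows would say little if slowing is 20% or less on average and log-SD is at most 0.15; the documents supply neither figure. How much information is lost overall cannot be determined from the documents. The stronger reading, that the 50% flag cannot detect neurotoxicity, is not supported: the Protocol reports seven active participants with a 50% SNAP loss.

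**What to change.** In SAP 2.7.4.6, for each of the four parameters, by arm and visit:
- Tabulate the number tested, raw value, change and % change from baseline, with on/off-treatment status. Use the geometric mean ratio to baseline for amplitudes.
- Add an individual trajectory plot.
- List all NCS data, not only those with findings.
- Keep the 50% count and recovery rows, but not as the only result for velocity. Define partial recovery or drop it from the table.
- Keep any active–placebo difference descriptive and limit it to visits where placebo was re-tested. Note that retests before the safety measure were triggered by findings and that placebo follow-up ends by Week 33.

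The cost is SAP wording and a few more outputs from data already collected and largely derived.
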